**Table 5-8      Prohibited medication (Please also see Appendix 9)**

Medication	Prohibition period	Action taken
ACEIs Inhibitors: benazepril, enalapril, Lisinopril, captopril, Ramipril, Fosinopril, Moexipril Quinapril, Trandolapril	Duration of study	Discontinue study treatment
Aliskiren (only subjects with concurrent diabetes)	Duration of study	Discontinue study treatment
Bile acid sequestering agents (such as cholestyramine or colestipol)	Duration of study	Switch to alternate agent to avoid interference with study drug absorption. If use of alternate agent is not appropriate, do not randomize or discontinue study drug treatment.
Nesiritide and intravenous nitrates	Duration of study	Do not randomize. If hospitalized, either interrupt or discontinue study treatment. Nesiritide and intravenous nitrates have not been studied. Oral, topical and sublingual nitrates are permissible.
Prescription and non-prescription medications taken for insomnia or to induce sleep (See Appendix 9 for details and examples)	Duration of study	Discontinue study treatment

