#### **4.2 Exclusion criteria**

Subjects fulfilling any of the following criteria are not eligible for inclusion in this study. No additional exclusions may be applied by the investigator, in order to ensure that the study population will be representative of all eligible subjects.

1. Subjects with a history of hypersensitivity to any of the study drugs, including history of hypersensitivity to drugs of similar chemical classes, or allergy to ACEIs, ARBs, or NEP inhibitors as well as known or suspected contraindications to the study drugs.
2. Subjects with a history of angioedema drug related or otherwise
3. Subjects with symptomatic hypotension or systolic blood pressure  $<$ 100 mmHg at screening or  $<$ 95 mmHg at randomization.
4. Subjects with any conditions in skin or upper extremities which would limit the ability to tolerate a wrist-worn actigraphy device on the nondominant arm for 24 hours/day for the duration of the study.
5. Subjects unwilling or unable to wear and operate the study measurement devices for the phases required.
6. Subjects who are currently hospitalized, or were discharged from the hospital within 4 weeks prior to enrollment.
7. Subjects who are already taking sacubitril/valsartan
8. Subjects who are nonambulatory or use mobility assistive devices such as motorized devices, wheelchairs, or walkers. The use of canes for stability while ambulating is acceptable.
9. Subjects with physical activity impairment primarily due to conditions other than heart failure such as:
  - Exertional angina
  - inflammatory or degenerative joint disease
  - gout
  - peripheral vascular disease

- neurologic diseases affecting activity or mobility

10. Subjects with nontypical circadian behavioral patterns (for example: shift workers actively rotating shifts, subjects with non-24-hour sleep wake disorder as result of blindness)

11. Subjects with tremor, rigor or mobility limitations affecting the nondominant arm (e.g. due to Parkinson's disease, joint contractures, paralysis, injury etc.)

12. Subjects with chronic obstructive pulmonary disease (COPD) who require supplemental oxygen.

13. Subjects using a continuous positive airway pressure (CPAP) devices or similar technology for treatment of sleep disorders

14. Subjects unwilling or unable to refrain from the use of prescription and/or over the counter (OTC) sleep aids for the duration of the study

15. Subjects with body mass index (BMI) > 35

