### **5.5.8 Prohibited medication**

Use of the treatments displayed in the table below and [Appendix 9](#) is NOT allowed after the baseline phase. Please note the list of prohibited medication is not exhaustive. If you have any questions, the medical monitor should be contacted.

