### **5.6.2 Discontinuation of study treatment**

Subjects may voluntarily discontinue the study drug for any reason at any time.

Study drug must be discontinued under the following circumstances:

- Withdrawal of consent
- Pregnancy
- Use of prohibited concomitant medication
- Any protocol deviation that constitutes a risk to the subject
- Investigator believes that continuation of study drug may be detrimental to the subject's well-being
- Study medication may be discontinued at the investigator's discretion if any of the following occur:
  - Any severe suspected drug related AE
  - Suspected occurrence of angioedema. A subject with any signs or symptoms of clinically significant angioedema should be thoroughly evaluated by the investigator to determine if it constitutes a reason for discontinuation of study medication.

Depending on the serum potassium, blood pressure, or eGFR, subjects may need to have their study drug dose or the dose of another concomitant medication reduced or discontinued; or, if appropriate, have potentially contributing agents adjusted. Refer to appendices for treatment guidelines for hyperkalemia, hypotension or renal dysfunction, respectively.

In the case of study drug discontinuation, every effort must be made to complete an end of study visit and obtain follow up health status information for any subjects that withdraw from the

study. If the subject refuses, he/she should be contacted by telephone in place of protocol-specified visits unless the subject expressly refuses such contacts.

The investigator must notify the sponsor of any study drug discontinuation and record it on the Dosage Administration Record eCRF.

If discontinuation of study treatment occurs, the subject should NOT be considered withdrawn from the study. The subject should return to the clinic as soon as possible, after discontinuation of study drug, for an end of study visit. All assessments from the final visit (Visit 13) in the visit schedule of assessments ([Table 6-1](#)) must be completed and recorded in the eCRF. The Study Completion eCRF will also need to be completed. The investigator must determine the primary reason for the subject's premature discontinuation of study treatment and record this information in the eCRF.

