## 21 Appendix 9: Prohibited Medications: Prescription and non-prescription medications taken for insomnia or to induce sleep

CATAGORY	EXAMPLES
Benzodiazepines with sedating properties for insomnia; or alternative indications taken at bedtime	Examples include: Alprazolam (Xanax) Clonazepam (Clozaril) Diazepam (Valium) Estazolam (Prosom) Flurazepam (Dalmane) Lorazepam (Ativan) Quazepam (Doral) Oxazepam (Serax) Temazepam (Restoril) Triazolam (Halcion)
Non-benzodiazepines for insomnia	Examples include: Eszopiclone (Lunesta) Ramelteon (Rozerem) Suvorexant (Belsomra) Tasimelteon (Hetlioz) Zaleplon (Sonata) Zolpidem (Ambien, Ambien CR, Edluar, Intermezzo, Zolpimist)
Antidepressants with sedating properties for insomnia; or alternative indications taken at bedtime	Examples include: Amitriptyline (Elavil), Doxepin (Silenor, Sinequan) Mirtazapine (Remeron) Trazodone (Oleptro, Desyrel)
Other prescriptions with sedating properties for insomnia; or alternative indications taken at bedtime	Examples include: Baclofen (Lioresal, Gablofen) Cyclobenzaprine (Flexeril) Gabapentin (Neurontin) Hydroxyzine (Atarax) Olanzapine (Zyprexa) Phenobarbital (Phenobarb) Quetiapine (Seroquel) Tiagabine (Gabitril)
Non-prescription Drugs for sleep/insomnia or designated for "nighttime" or "PM" use containing any of the following active ingredients: Diphenhydramine, Doxylamine, Chlorpheniramine	Examples include: Advil P.M. Aleve P.M. Benadryl Chlorphen Nytol Nyquil Sominex Tylenol P.M Unisom ZzzQuil
Non-prescription Herbs/Supplements for sleep/insomnia or designated for "nighttime" or "PM"	Examples include: 5-HTP Kava Kava Melatonin Valerian Root

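### Exclusion 14 screens only for sleep aids, while Appendix 9 also bans sedating drugs taken at bedtime for other reasons, so an eligible patient can be randomized into a required stop of study drug

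*Protocol*

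**What the plan says.** **Eligibility.** Exclusion 14 in protocol Section 4.2 reads "Subjects unwilling or unable to refrain from the use of prescription and/or over the counter (OTC) sleep aids for the duration of the study". The same section opens by stating "No additional exclusions may be applied by the investigator".

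**Prohibition.** Section 5.5.8 says that use of the treatments in Table 5-8 and in Appendix 9 "is NOT allowed after the baseline phase". The sleep row of Table 5-8 covers "Prescription and non-prescription medications taken for insomnia or to induce sleep (See Appendix 9 for details and examples", with discontinuation of study treatment as the action. Section 5.6.2 lists "Use of prohibited concomitant medication" among the circumstances in which study drug must be stopped.

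**Appendix 9.** The title is limited to drugs taken for insomnia or sleep. Three category headings are wider:
- "Benzodiazepines with sedating properties for insomnia; or alternative indications taken at bedtime"
- "Antidepressants with sedating properties for insomnia; or alternative indications taken at bedtime"
- "Other prescriptions with sedating properties for insomnia; or alternative indications taken at bedtime"

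The examples in these three categories include gabapentin, baclofen, quetiapine and amitriptyline.

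**The concern.** Exclusion 14 and Appendix 9 do not cover the same drugs. A bedtime prescription for something other than sleep can pass screening and then be prohibited once the baseline phase ends. The use is knowable at Visit 1, yet the protocol deals with it by stopping study drug after randomization.

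At stake is the primary measurement. A patient who stops study drug is called in for an end-of-study visit, so the Week 8 actigraphy may never be collected. Because sleep aids is undefined, sites may also differ on how far exclusion 14 reaches. Similar patients could then be screened out at one center and randomized at another.

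**Working it through.** No figure in the plan bears on this point, so the check compares the passages.

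1. **Scope at screening.** Exclusion 14 names sleep aids, prescription or over the counter. It gives no definition and no cross-reference to Appendix 9.

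2. **Scope of the ban.** Section 5.5.8 applies to Table 5-8 and Appendix 9 together. The table's title and its sleep row both point to the appendix. Appendix 9 is therefore part of the prohibition.

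3. **Scope inside Appendix 9.** There are six categories. Three stay with sleep: non-benzodiazepine hypnotics, and non-prescription drugs and herbal products for sleep or night-time use. The other three (benzodiazepines, antidepressants, other prescriptions) add bedtime use for a different indication, which goes beyond the appendix's own title.

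4. **One patient followed through.** Take a patient on nightly gabapentin for pain, not for sleep.
   - *Eligibility:* in ordinary language this is not a sleep aid, so exclusion 14 does not clearly apply. No other criterion in Section 4.2 addresses a sedating drug taken for another purpose. Exclusion 9 would remove the patient only if the painful condition were the main cause of limited activity. The investigator may not add an exclusion.
   - *After the baseline phase:* the drug is a named example in the third of the wider categories, so it is prohibited.
   - *Consequence:* the Table 5-8 action and the mandatory list in Section 5.6.2 both lead to stopping study drug if the use continues.

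5. **Comparison with other Table 5-8 rows.** Aliskiren in diabetes, nesiritide and bile acid sequestrants are matched by exclusions 17, 18 and 19. The nesiritide and bile acid rows also tell the site not to randomize (for bile acids, when an alternative agent is unsuitable). The sleep row has no such instruction, and its exclusion is narrower than its appendix.

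6. **Effect on the primary endpoint.** Section 5.6.2 brings the patient in for an end-of-study visit as soon as possible after stopping. Section 2 sets the measurement weeks at -1, 1, 8, 9 and 16, and Section 3.2 keeps data from other periods out of the defined endpoints. Week 1 is therefore the only planned post-baseline measurement before Week 8. Under protocol Section 9.4.3 and SAP Section 2.5.3 there are two outcomes when Week 8 is missing:
   - With an evaluable Week 1 value, LOCF carries it to Week 8. That value comes from the starting dose level, because the first scheduled titration is at Week 2 (Table 5-5).
   - With no post-baseline value, the patient is removed from the analysis. SAP Section 2.5.1 requires at least 5 of 7 days of data for a weekly mean, so a very early stop could end here.

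**The case against.** **There is a check before randomization.** Section 5.5.7 requires each concomitant drug to be assessed against the exclusion criteria and the prohibited list, with a call to the medical monitor before randomizing if in doubt. Section 5.5.8 also offers the medical monitor for questions. This stands as a real reduction in risk, since the drug should come to light. But it creates no exclusion criterion, and Section 4.2 bars the site from adding one.

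**Prohibited but not excluded need not mean randomize and then stop.** The ACE-inhibitor row carries the same action and has no matching exclusion, yet the design plainly admits current users. This stands in part: the forced stop arises only if the patient is still taking the drug after the baseline phase. However, for ACE inhibitors the protocol describes the withholding period, and exclusion 14 asks about willingness to refrain from sleep aids. Nothing comparable covers bedtime drugs taken for another indication.

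**Sleep aids could be read to include everything in Appendix 9.** This is possible, because the term is undefined. But exclusion 14 does not say so, and a drug taken for pain or depression is not ordinarily called a sleep aid.

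**Two stronger readings go too far.** A reader might infer that the Table 5-8 wording permits these drugs while Appendix 9 forbids them. The documents do not support that: Section 5.5.8, the table title and the row itself all bring in Appendix 9. The gap is between exclusion 14 and the appendix. A reader might also infer a loss of power for the primary comparison. That would need a prevalence the documents do not give, and it would need every affected patient to be lost, although LOCF keeps anyone with a Week 1 value. The planned 20% drop-out and 10% non-evaluable allowances could also absorb some of these cases. In addition, Section 5.6.2 says that stopping study drug is not withdrawal from the study.

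**Conclusion.** The concern holds as a mismatch between exclusion 14 and Appendix 9, together with category headings in Appendix 9 that exceed its title. An eligible patient can be randomized and then fall under a ban whose stated action is to stop study drug. Week 8 can then be missing, or be filled with a Week 1 value.

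The size is unknown. The conclusion rests on the ordinary meaning of sleep aids, on the patient continuing the bedtime drug after the baseline phase, and on the Section 5.5.7 check not resolving the case first. Which scope is clinically right is not judged here. This is a cheap improvement and does not by itself threaten the trial's conclusions.

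**What to change.** Reconcile exclusion 14, the sleep row of Table 5-8, and the title and category headings of Appendix 9, so that all describe the same set of drugs and indications and eligibility agrees with the prohibition. One way is to have exclusion 14 refer to the reconciled Appendix 9 list. The sponsor's clinical team must choose the scope.

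The cost is amendment wording in these three places. If the wider scope is kept, slightly fewer patients will be eligible.

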### 5.5.9      Emergency breaking of assigned treatment code

Emergency code breaks must only be undertaken when it is required to in order to treat the patient safely. Most often, study treatment discontinuation and knowledge of the possible treatment assignments are sufficient to treat a study patient who presents with an emergency condition. Emergency treatment code breaks are performed using the IRT. When the investigator contacts the system to break a treatment code for a patient, he/she must provide the requested patient identifying information and confirm the necessity to break the treatment code for the patient. The investigator will then receive details of the investigational drug treatment for the specified patient and a fax or email confirming this information. The system will automatically inform the Novartis monitor for the site and the Study Team that the code has been broken.

It is the investigator's responsibility to ensure that there is a dependable procedure in place to allow access to the IRT/code break cards at any time in case of emergency. The investigator will provide:

- protocol number
- study drug name (if available)
- patient number

In addition, oral and written information to the subject must be provided on how to contact his/her backup in cases of emergency, or when he/she is unavailable, to ensure that un-blinding can be performed at any time.

## **5.6 Study completion and discontinuation**

### **5.6.1 Study completion and post-study treatment**

A subject will be considered to have completed the study when the subject has completed the last visit planned in the protocol (Visit 13). At the end of study visit, subjects will be asked to return all remaining study drug. The investigator must provide follow-up medical care for all subjects who are prematurely withdrawn from the study, or must refer them for appropriate ongoing care.

### **5.6.2 Discontinuation of study treatment**

Subjects may voluntarily discontinue the study drug for any reason at any time.

Study drug must be discontinued under the following circumstances:

- Withdrawal of consent
- Pregnancy
- Use of prohibited concomitant medication
- Any protocol deviation that constitutes a risk to the subject
- Investigator believes that continuation of study drug may be detrimental to the subject's well-being
- Study medication may be discontinued at the investigator's discretion if any of the following occur:
  - Any severe suspected drug related AE
  - Suspected occurrence of angioedema. A subject with any signs or symptoms of clinically significant angioedema should be thoroughly evaluated by the investigator to determine if it constitutes a reason for discontinuation of study medication.

Depending on the serum potassium, blood pressure, or eGFR, subjects may need to have their study drug dose or the dose of another concomitant medication reduced or discontinued; or, if appropriate, have potentially contributing agents adjusted. Refer to appendices for treatment guidelines for hyperkalemia, hypotension or renal dysfunction, respectively.

In the case of study drug discontinuation, every effort must be made to complete an end of study visit and obtain follow up health status information for any subjects that withdraw from the

study. If the subject refuses, he/she should be contacted by telephone in place of protocol-specified visits unless the subject expressly refuses such contacts.

The investigator must notify the sponsor of any study drug discontinuation and record it on the Dosage Administration Record eCRF.

If discontinuation of study treatment occurs, the subject should NOT be considered withdrawn from the study. The subject should return to the clinic as soon as possible, after discontinuation of study drug, for an end of study visit. All assessments from the final visit (Visit 13) in the visit schedule of assessments ([Table 6-1](#)) must be completed and recorded in the eCRF. The Study Completion eCRF will also need to be completed. The investigator must determine the primary reason for the subject's premature discontinuation of study treatment and record this information in the eCRF.

If the subject cannot or is unwilling to attend any visit(s), the site staff should maintain regular telephone contact with the subject, or with a person pre-designated by the subject. This telephone contact should preferably be done according to the study visit schedule.

The investigator must also contact the sponsor to register the subject's discontinuation from study treatment.

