### **5.5.5 Permitted dose adjustments and interruptions of study treatment**

Every attempt should be made to maintain subjects on the target study drug dose level for as long as possible throughout the study. If, however, in the opinion of the investigator, a subject is unable to tolerate the protocol-specified target dose, the investigator should consider whether dose adjustments of concomitant medications may rectify the situation before reducing the dose of study treatment. If adjustment of the concomitant medications is not possible or does not alleviate the side effects of concern, the investigator may down-titrate the dose of the study drug to the previous dose level. If needed, the study drug may be stopped completely, if this occurs, the subject should return to the clinic as soon as possible, after discontinuation of study drug, for an end of study visit. Subjects may restart their current dose of study drug following an interruption of treatment, based on investigator judgment.

Study drug dose level adjustments should be mainly based on overall safety and tolerability with special focus on:

- Hyperkalemia
- Symptomatic hypotension
- Clinically significant decrease in eGFR/increase in serum creatinine (defined as a serum creatinine of  $\geq 0.5\text{mg/dl}$  with at least a 25% decrease in eGFR).

These changes must be recorded on the Dosage Administration Record CRF.

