**Table 6-1** **Assessment schedule**

Phase	Screening/Baseline		Randomized Treatment						Open Label Extension				Unscheduled ◊	
Visit Number	1	2	3	4	5	6	7	8	9	10	11	12	13/EOS	
Days	- Day 14	- Day 7 to - Day 1	Day 1	Day 7	Day 14	Day 28	Day 42	Day 56	Day 63	Day 70	Day 84	Day 98	Day 112	UNSCHED
Time of Visit	Week -2	Week -1	Day 1	Week 1	Week 2	Week 4	Week 6	Week 8	Week 9	Week 10	Week 12	Week 14	Week 16	UNSCHED
Visit type	Office	Tele-visit	Office (randomization)	Tele-visit	Office	Office	Tele-visit	Office	Tele-visit	Office	Office	Tele-visit	Office	Office
Titration					X	X		X		X	X			
Laboratory Evaluations (per protocol) 	X		X		X			X		X			X	X
Urine pregnancy (site) 	X													
Serum pregnancy			X			X		X			X		X	
Open label titration for control arm								X (control only)						
Randomization			X											
Sensor use training 	S													
ActiWatch Exchange & Data Upload			X			X		X			X		X	

Phase	Screening/Baseline		Randomized Treatment						Open Label Extension				Unscheduled ◊	
Visit Number	1	2	3	4	5	6	7	8	9	10	11	12	13/EOS	
Days	- Day 14	- Day 7 to - Day 1	Day 1	Day 7	Day 14	Day 28	Day 42	Day 56	Day 63	Day 70	Day 84	Day 98	Day 112	UNSCHED
Time of Visit	Week -2	Week -1	Day 1	Week 1	Week 2	Week 4	Week 6	Week 8	Week 9	Week 10	Week 12	Week 14	Week 16	UNSCHED
Visit type	Office	Tele-visit	Office (randomization)	Tele-visit	Office	Office	Tele-visit	Office	Tele-visit	Office	Office	Tele-visit	Office	Office
Adverse Events/Serious Adverse Events §	X	X §	X	X §	X	X	X §	X	X §	X	X	X §	X	X
Concomitant Medications	X	X	X	X	X	X	X	X	X	X	X	X	X	X
Dosage Administration Record			X		X	X		X		X	X		X	X
Drug Accountability					S	S		S		S	S		S	S
IRT Call	X		X		X	X		X		X	X		X	X
Study Completion/Early Termination													X	
Angioedema Assessments	X		X		X	X		X		X	X		X	X

\*\*IC must be obtained prior to all study specific screening procedures during or as close to the start of the screening phase as possible  
 ◊ = Unscheduled visit assessments marked with (X) are optional procedures that may be performed at the investigators discretion, or if the patient withdraws early from treatment or study.  
 X = assessment to be recorded on clinical data base  
 S = assessment to be documented in source data  
 1. Height should be measured in centimeters if possible  

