## **9 Data analysis**

The analysis will be conducted on all subject data at the time the trial ends. Any data analysis carried out independently by the investigator should be submitted to Novartis before publication or presentation.

A designated Contract Research Organization will perform the statistical analysis.

It is planned that the data from all centers that participate in this protocol will be combined, so that an adequate number of subjects will be available for analysis.

Unless otherwise specified, all statistical tests will be conducted against a two-sided alternative hypothesis, employing a significance level of 0.05.

Efficacy, safety, and other data will be summarized. For continuous variables, summary statistics (mean, standard deviation, median, 25th and 75th percentiles, interquartile range, minimum, and maximum) at each time point and for change from baseline to each time point will be reported by treatment group. Discrete variables will be summarized by frequencies and percentages.

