### **9.1 Analysis sets**

The following subject sets will be used for the statistical reporting and analyses:

The Randomized Set will consist of all randomized subjects.

The Full Analysis Set (FAS) will consist of all subjects with the exception for those subjects who have not been qualified for randomization and have not received study drug, but have been inadvertently randomized into the study. Following the intent-to-treat principle, subjects will be analyzed according to the treatment to which they were assigned at randomization. Efficacy variables will be analyzed based on the FAS as the primary set.

The Safety Set (SAF) will consist of all randomized subjects who received at least one dose of study drug. Subjects will be included in the analysis according to the treatment actually received. The Safety Set will be used for the analyses of safety variables.

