## **9.8 Sample size calculation**

Primary endpoint:

Assuming a significance level of 0.05, a total sample size of 136 subjects would provide 90% power to detect a difference of 5000 in the change from baseline in mean activity counts collected during the most active 30 minutes between the sacubitril/valsartan treatment group and the enalapril group during Week 8, assuming a common standard deviation of 7400 (Maurer 2009) and a 20% drop-out rate and a 10% rate of subjects with non-evaluable data. The assumed effect size of 68% (5000/7400) will be maintained in the event the log transformation is needed for the primary analysis thus not affecting the sample size calculation and power of the study.

Secondary endpoint:

Assuming a significance level of 0.05, a sample size of 136 subjects would provide 93% power to detect a 3.5 point difference in the change from baseline in mean activity value during the sleep (expressed as counts per minute) between the sacubitril/valsartan treatment group and the enalapril group during Week 8, assuming a common standard deviation of 4.9 and a 20% drop-out rate and a 10% rate of subjects with non-evaluable data (Peterson 2012).

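### The protocol keeps patients who stop study drug in the study but makes no provision to record their Week 8 actigraphy, so the primary analysis must carry forward Week 1 or drop them

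*Protocol*

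**What the plan says.** **Status after stopping.** Protocol 5.6.2 says that when study treatment is discontinued "the subject should NOT be considered withdrawn from the study". It continues: "The subject should return to the clinic as soon as possible, after discontinuation of study drug, for an end of study visit". All Visit 13 assessments and the Study Completion eCRF are required at that visit. Section 5.5.5 gives the same instruction for a complete stop. Section 5.6.1 defines Visit 13 as the point at which the study is complete.

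**Contact afterwards.** Section 5.6.2 describes follow-up of health status and telephone contact, preferably on the visit schedule, for patients who refuse or cannot attend visits. Neither document mentions device wear or a Week 8 recording after the end-of-study visit.

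**Endpoint and analysis.** The primary endpoint needs Week 8 actigraphy (Protocol 9.4.1), with at least 5 valid days in the week (SAP 2.5.1). The efficacy set is the FAS: "Following the intent-to-treat principle, subjects will be analyzed according to the treatment to which they were assigned at randomization". SAP 5.6, Table 2, excludes nobody for stopping drug. A missing Week 8 value is filled by LOCF, and a patient with no post-baseline value is removed (Protocol 9.4.3, SAP 2.5.3). The measurement weeks are -1, 1, 8, 9 and 16 (Protocol 2), and data from other periods are not used for the defined endpoints (Protocol 3.2).

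**The concern.** The primary outcome of a patient who stops drug early is replaced rather than measured. The documented reasons for stopping include poor tolerability (5.5.5), worsening heart failure (5.5.6), severe suspected drug-related events (5.6.2) and prohibited medication, including sleep aids (Table 5-8). Several of these bear directly on physical activity, so the missing values are unlikely to be a random subset.

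The replacement is also weak. Week 1 precedes the first titration at Week 2 (Table 5-5), and it precedes whatever led a later stopper to stop. The supportive analyses in SAP 2.5.4 are a Wilcoxon test and subgroups. Neither tests the missing-data assumption. Once the Week 8 window has passed without a recording, no analysis can recover it.

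**Working it through.** **1. The plan's own figure.** Inputs from Protocol 9 and 9.8: two-sided alpha 0.05; "a total sample size of 136 subjects would provide 90% power to detect a difference of 5000 in the change from baseline"; "assuming a common standard deviation of 7400"; 20% drop-out and 10% non-evaluable. Allocation is 1:1 (Protocol 5.2).

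- Normal approximation: n per arm = 2 x (1.960 + 1.282)^2 x (7400/5000)^2 = 46.03, so 47. Total 94/0.70 = 134.3, so 135.
- t-based: 48 per arm. Total 96/0.70 = 137.1, so 138.
- In reverse: 136 x 0.70 = 95.2 evaluable patients gives power 90.9% (normal) or 90.4% (t).

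The stated 136 and 90% are reproduced. The sample size is not at issue.

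**2. What enters the primary analysis, by time of permanent stop.**

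- Before 5 valid days in Week 1: if wear ends with the end-of-study visit, there is no post-baseline value and the patient is removed.
- From about Week 2 to Week 7: the only usable post-baseline week is Week 1. LOCF carries it forward, or the patient is removed if Week 1 is not evaluable.
- Late in Week 8, with 5 valid days already recorded: the measured value is used and the problem does not arise.
- Temporary interruption with restart (5.5.5): the patient stays on the visit schedule and the problem does not arise.

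**3. How many.** 136 x 0.20 = 27.2 patients, or 68 x 0.20 = 13.6 per arm. Treating all of them as drug stoppers is an assumption, since drop-out also covers withdrawn consent and loss to follow-up.

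**4. Illustrative bias.** Take as target the Week 8 outcome whether or not the patient is still on drug. Let p be the proportion stopping in each arm and D the carried-forward value minus the true Week 8 value. Then

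bias = p_T x D_T - p_C x D_C.

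The documents give neither D nor separate stopping rates by arm. I assume D = 1000 to 5000 counts.

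- Equal rates (20%/20%) and equal D: bias = 0.
- Rates 15 points apart, for example 12.5% and 27.5% (average 20%), equal D: 0.15 x 1000 = 150 to 0.15 x 5000 = 750 counts. Divided by 5000, this is 3% to 15% of the target difference.

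The sign depends on which arm stops more and on the direction of D.

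**5. Effect on the test, with no true difference.** Take D = 5000 in size and 68 x 0.90 = 61.2 analysed per arm. The standard error is 7400 x sqrt(2/61.2), about 1338 counts.

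- 20% against 20%: bias 0, rejection rate 5.0%.
- 15% against 25%: bias 500, rejection rate about 6.6%.
- 10% against 30%: bias 1000, rejection rate about 11.6%.

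**The case against.** The strongest reply is that the text is ambiguous and does not forbid the recording. Table 6-1 and Section 6.6.4 speak of exchanging the watch, and no sentence says it is taken back at the end-of-study visit. Section 6.6.4 has it worn for the whole study. Telephone contact is the fallback for patients who will not or cannot attend, which may imply that other patients keep attending. This stands: a reader might infer that Week 8 actigraphy is never recorded after a stop, but the documents show only that nothing provides for it.

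A reader might also infer from the Table 6-1 footnote that a site could skip the upload at an early exit and lose even Week 1. The footnote calls the unscheduled items "optional procedures that may be performed at the investigators discretion, or if the patient withdraws early from treatment or study", and that column has no Actiwatch upload. However, the Study Completion/Early Termination row is marked only under 13/EOS, which does include the upload, and 5.6.2 makes the Visit 13 assessments mandatory. The loss would need a site to overlook both, so the footnote merits only a clarification.

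The sentence on intent-to-treat concerns analysis by assigned arm. It does not promise follow-up after stopping, and the plan openly allows for missing data. That is fair. The remaining conflict is between a patient who is still in the study and a visit that closes the study for that patient.

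**Conclusion.** The point holds as a gap that should be fixed, not as a fatal flaw. The status given in 5.6.2 and the end-of-study visit in 5.6.2 and 5.5.5 do not fit together. Followed as written, they leave the primary analysis with a Dose Level 1 value from Week 1, or no value, for patients who stop permanently between about Week 2 and Week 7.

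The possible bias runs from zero, with equal stopping rates and equal D in both arms, to 150 to 750 counts with a 15-point difference in stopping. The figures rest on an assumed D, an assumed imbalance and the assumption that all drop-outs are stoppers. They do not show that the result will be biased. They show that the plan would not collect the data needed to tell.

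**What to change.** Reconcile the passages on status after stopping with those on the end-of-study visit, and state whether Week 8 actigraphy is collected.

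- **Protocol 5.5.5, 5.6.2 and Table 6-1:** keep the prompt post-discontinuation visit and its safety assessments exactly as written. Add that a patient who stops drug before Week 8 and has not withdrawn consent keeps wearing the Actiwatch through Week 8, with the Visit 6 and Visit 8 exchange and upload. No rule on when treatment stops is affected.
- **SAP 2.5:** use the recorded Week 8 value in the FAS whether or not the patient is on drug, and apply LOCF only where that value is truly missing.
- **Table 6-1 footnote (minor):** align it with 5.6.2 so that Actiwatch data are uploaded at any early exit.

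The cost is a protocol amendment and two SAP sentences. The device, the continuous wear and both visits already exist. Some patients will decline, and some Week 8 values will reflect no drug or switched therapy.

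The effect on power can be illustrated. Suppose all of the 20% are followed and only the 10% non-evaluable are lost (61.2 per arm), and stoppers keep a fraction f of the effect. The difference is then 5000 x (0.8 + 0.2f). Power by t test is 84.3% for f = 0 (4000 counts), 91.6% for f = 0.5 (4500) and 96.0% for f = 1 (5000). The documents give no value of f.
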